## 7.0 INVESTIGATIONAL AND ANALYSIS PLAN

### 7.1 Overall Trial Design

This is an exploratory, multi-site, nonrandomized, open label, prospective, interventional, single-arm, study to evaluate the correlation of serum soluble ST2 levels with clinical, endoscopic and histological activity in subjects with moderate to severe active UC who received golimumab. During this study, golimumab will be used according to the SmPC.

The overall study design is illustrated in the trial design diagram presented in **Section 2.1**. Study procedures are outlined by visit in the trial flow chart in **Section 2.2**.

After signing the informed consent, subjects will enter a screening period of up to 42 days. After confirmation of eligibility criteria, subjects will initiate treatment with golimumab according to SmPC (Baseline Visit – V2). Subjects will be followed for a period of 16 weeks for clinical assessments and data collection. Biomarker samples (ST2 and fecal calprotectin) will be collected at baseline and at all subsequent visits. All subjects will be evaluated for clinical, endoscopic (fibrosigmoidoscopy) and histologic activity at screening, week 6 and week 16.

The trial design is appropriate for the indication studied. Validated methods of data collection, analysis, and evaluation will be used for the trial.

The method of assessment of serum soluble ST2 is described in **Section 7.6**.

In addition it will be evaluated the correlation between ST2 levels with fecal calprotectin, which is currently the best surrogate marker for the presence of intestinal inflammation. Fecal calprotectin has been demonstrated to be a sensitive and specific marker in identifying intestinal inflammation and response to treatment in subjects with IBD.

The Geboes index is a validated instrument for evaluating histologic disease activity in UC (Geboes et al., 2000) - see more detailed information in **Section 7.7.2.2**. This index will be applied at screening, week 6 and week 16 in order to determine if a correlation exists between its overall score and serum soluble ST2 levels at the respective time points.

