Ulcerative Colitis Endoscopic Index of Severity (UCEIS) is a 3-item validated tool for assessing endoscopic severity of UC (Travis et al., 2011) - see more detailed information in **Section 7.7.2.2** and Appendix 4. This tool will be applied at screening, week 6 and week 16 in order to determine if a correlation exists between its overall score and the endoscopic Mayo score at the respective time points.

At this moment, little is known about the benefit of measuring golimumab serum concentrations in daily practice. In the pivotal PURSUIT Induction trial, an exposure-response relationship was observed for the change from baseline in Mayo score and rates of clinical response and clinical remission, with patients in the highest serum golimumab concentration quartiles having greater improvement in median Mayo scores and greater rates of clinical response and clinical remission when compared with those in the lower quartiles at week 6 (Sandborn et al., 2014a). A second study, also including UC patients from PURSUIT (Sandborn et al., 2016a and Sandborn et al., 2016b), assessed golimumab pharmacokinetics and exposure-response relationship. It was observed that serum golimumab concentrations are approximately dose proportional, and a positive serum golimumab concentration-efficacy relationship exists during induction/maintenance golimumab treatment of adult UC patients (Adedokun et al., 2016).

On the other hand, the presence of anti-drug antibodies may also be associated with low response to anti-TNFs since it is thought that anti-drug antibodies can neutralize the therapeutic antibodies or induce their rapid elimination (Vincent et al., 2013). To investigate these findings, comparisons of serum golimumab levels and the presence of anti-golimumab antibodies with clinical response and remission, endoscopic activity, fecal calprotectin and histological activity will be analysed as exploratory endpoints.

Serum golimumab levels and the presence of anti-golimumab antibodies will be evaluated at week 6 and week 16 using an ELISA (enzyme-linked immunosorbent assay) technique (IDKmonitor® Golimumab drug level ELISA and IDKmonitor® golimumab free ADA ELISA, from Immundiagnostik AG, Germany). These analyses will be done at the end of the study and will not be available to the investigators during subjects' participation in the study.

Considering these study aims, there is no justification for including a comparative arm.

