#### 7.7.3.3 Exploratory endpoints

- To compare serum golimumab levels with clinical activity (total Mayo score) at weeks 6 and 16.
- To compare serum golimumab levels in subjects with endoscopic active disease (total Mayo score  $>2$ ) and subjects with inactive disease (total Mayo score  $\leq 2$  points with no individual subscore  $>1$ ) at week 6 and 16.
- To compare the presence of anti-golimumab antibodies (+ or -) and clinical activity (total Mayo score) at weeks 6 and 16.
- To compare the presence of anti-golimumab antibodies in subjects with endoscopic active disease (total Mayo score  $>2$ ) and subjects with inactive disease (total Mayo score  $\leq 2$  points with no individual subscore  $>1$ ) at week 6 and 16.
- To compare serum golimumab levels with endoscopic activity (endoscopic Mayo score) at weeks 6 and 16.
- To compare the presence of anti-golimumab antibodies (+ or -) and endoscopic activity (endoscopic Mayo score) at weeks 6 and 16.
- To compare serum golimumab levels with faecal calprotectin at weeks 6 and 16.
- To compare the presence of anti-golimumab antibodies (+ or -) and faecal calprotectin at weeks 6 and 16.
- To compare serum golimumab levels with histological activity (Geboes index) at weeks 6 and 16.
- To compare the presence of anti-golimumab antibodies (+ or -) and histological activity (Geboes index) at weeks 6 and 16.

- To compare quartile serum golimumab levels with rates of clinical response and clinical remission
- To compare serum golimumab levels between subjects who achieved response at week 6 and subjects who did not.
- To compare serum golimumab levels among subjects who achieved response at week 16 and subjects who did not.
- To compare the presence of anti-golimumab antibodies among subjects who achieved response at week 6 and subjects who did not.
- To compare the presence of anti-golimumab antibodies who achieved response at week 16 and subjects who did not.
- To compare serum golimumab levels between subjects who achieved remission at week 6 and subjects who did not.
- To compare serum golimumab levels among subjects who achieved remission at week 16 and subjects who did not.
- To compare the presence of anti-golimumab antibodies among subjects who achieved remission at week 6 and subjects who did not.
- To compare the presence of anti-golimumab antibodies who achieved remission at week 16 and subjects who did not.

See **Section 7.7.2.2** for the definitions of interest.

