- The association between the presence of anti-golimumab antibodies at week 6 and week 16 and clinical activity (total Mayo score) at the same time points will be tested through t-test for independent samples or the Mann-Whitney non-parametric test, according to the assumption validations of the statistical test.
- Presence of anti-golimumab antibodies will be compared between patients with active disease (total Mayo score  $>2$ ) and patients with inactive disease (total Mayo score  $\leq 2$  points with no individual subscore  $> 1$ ) at week 6 and 16 through Chi-Square test or Fisher exact test.
- Serum golimumab levels at week 6 and week 16 will be correlated with endoscopic activity (endoscopic Mayo score) at the same time points, through Spearman correlation coefficient.

- The association between the presence of anti-golimumab antibodies at week 6 and week 16 and endoscopic activity (endoscopic Mayo score) at the same time points will be tested through t-test for independent samples or the Mann-Whitney non-parametric test, according to the assumption validations of the statistical test.
- Serum golimumab levels at Week 6 and Week 16 will be correlated with faecal calprotectin levels at the same time points through Pearson correlation coefficient or Spearman correlation coefficient in case the normality assumption was not verified.
- The association between the presence of anti-golimumab antibodies at Week 6 and Week 16 and faecal calprotectin levels at the same time points will be tested through will be tested through t-test for independent samples or the Mann-Whitney non-parametric test, according to the assumption validations of the statistical test.

Both measurements will be categorized by the cut-offs and Cohen's kappa coefficient will be obtained.

- The correlation between serum golimumab levels at week 6 and 16 and histological activity (measured by Geboes index score) at the same time points will be performed through the Spearman correlation coefficient.
- The association between the presence of anti-golimumab antibodies at week 6 and 16 and histological activity (measured by Geboes index score) at the same time points will be tested through Mann-Whitney non-parametric test.

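### Cohen's kappa is an unsuitable supplementary statistic for golimumab level or antibody status against faecal calprotectin; delete it or replace it with a labelled 2x2 analysis

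*Combined protocol and SAP*

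**What the plan says.** Two neighbouring items among the exploratory analyses of Section 8.0 involve calprotectin:

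- "Serum golimumab levels at Week 6 and Week 16 will be correlated with faecal calprotectin levels at the same time points", by Pearson or Spearman coefficient.
- "The association between the presence of anti-golimumab antibodies at Week 6 and Week 16 and faecal calprotectin levels", by t-test or Mann-Whitney test.

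A free-standing sentence follows the second item: "Both measurements will be categorized by the cut-offs and Cohen's kappa coefficient will be obtained". It does not name the two measurements. The plan gives no cut-off value for calprotectin or for golimumab level. Antibody status needs none, because Section 7.7.3.3 already treats it as binary: "To compare the presence of anti-golimumab antibodies (+ or -) and faecal calprotectin at weeks 6 and 16".

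Section 7.1 describes what each variable stands for:

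- Calprotectin is an inflammation marker: "fecal calprotectin, which is currently the best surrogate marker for the presence of intestinal inflammation".
- Antibodies are a possible cause of poor response, since "anti-drug antibodies can neutralize the therapeutic antibodies or induce their rapid elimination".
- Drug level is exposure, and the cited pharmacokinetic work reports that "a positive serum golimumab concentration-efficacy relationship exists during induction/maintenance golimumab treatment".

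Kappa appears in two other places in Section 8.0. The general paragraph assigns two categorical variables to chi-square or Fisher and then mentions kappa without a purpose. The secondary analyses apply kappa to ST2 and calprotectin, each categorised.

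**The concern.** Kappa is chance-corrected agreement between two classifications of one attribute. ST2 and calprotectin are both candidate markers of active disease, so asking whether they classify a subject alike makes sense. The same question has no meaning for antibody status or drug level against calprotectin. An antibody-positive subject with low calprotectin is not a case of two raters disagreeing.

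Two consequences follow. For antibodies, unequal margins put a ceiling on kappa that can be low even when every antibody-positive subject has raised calprotectin. For drug level, the rationale in Section 7.1 points to an inverse relation with inflammation, so the sign of kappa depends on whether high or low level is called positive, and the plan does not say which. What is at stake is one supplementary number in the exploratory report. Read on the usual agreement scale, it could understate a real relation or appear to conflict with the tests printed beside it.

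**Working it through.** **Inputs.** Section 8.0 expects 37 subjects. The documents give no antibody rate, no share with raised calprotectin and no cut-offs, so every margin below is an assumption.

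The plan states no target for kappa. Its only design figure is the 80% for the primary correlation. Taking 0.75 as the true correlation, Fisher's z gives Φ((atanh 0.75 − atanh 0.50)·√34 − 1.645) = Φ(0.825) = 79.5%. That figure reproduces and has no bearing on this point.

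**Formula.** kappa = (po − pe)/(1 − pe), where po is the observed and pe the chance proportion of matching classifications.

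**1. Ceiling with 3 of 37 antibody-positive.** Let p1 = 3/37 = 0.081 and let p2 be the share with raised calprotectin. Suppose every antibody-positive subject is raised. This is one-way dependence, because many antibody-negative subjects are raised too. Then po = p1 + (1 − p2) and pe = p1·p2 + (1 − p1)(1 − p2).

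| p2 | po | pe | maximum kappa |
|---|---|---|---|
| 0.40 | 0.681 | 0.584 | 0.23 |
| 0.50 | 0.581 | 0.500 | 0.16 |
| 0.60 | 0.481 | 0.416 | 0.11 |
| 0.70 | 0.381 | 0.332 | 0.07 |

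**2. Ceiling as the antibody count varies, same one-way dependence.**

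| Antibody-positive | 18/37 raised: kappa (Fisher p) | 26/37 raised: kappa (Fisher p) |
|---|---|---|
| 2 | 0.11 (0.23) | 0.05 (1.00) |
| 4 | 0.23 (0.046) | 0.10 (0.30) |
| 7 | 0.40 (0.003) | 0.18 (0.080) |
| 11 | 0.62 (<0.001) | 0.30 (0.015) |

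Example, 4 positive and 18 raised: po = (4 + 19)/37 = 0.622; pe = (4·18 + 33·19)/37² = 0.511; kappa = 0.111/0.489 = 0.23.

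The ceiling rises as the margins approach each other and reaches 1.00 when they are equal (for example, 11 positive and 11 raised).

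**3. Constant association, changing margin.** Hold the odds ratio at 6 with half the subjects raised. As the antibody-positive share goes 50%, 30%, 20%, 10%, 5%, kappa goes 0.42, 0.34, 0.25, 0.14, 0.07.

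**4. Drug level, illustrative table.** Raised calprotectin in 5 of 18 high-level and 14 of 19 low-level subjects.

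- High level called positive: po = 10/37 = 0.270; pe = (18·19 + 19·18)/37² = 0.500; kappa = −0.46.
- Low level called positive: po = 27/37 = 0.730; pe = (19·19 + 18·18)/37² = 0.500; kappa = +0.46.
- Odds ratio = (5·5)/(13·14) = 0.14; Fisher p = 0.009.

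**5. Recoding can change size as well as sign.** Take 4 antibody-positive, all among 26 raised.

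- Antibody presence called positive: po = 15/37 = 555/1369; pe = (4·26 + 33·11)/1369 = 467/1369; kappa = 88/902 = 0.10.
- Antibody absence called positive: po = 22/37 = 814/1369; pe = (33·26 + 4·11)/1369 = 902/1369; kappa = −88/467 = −0.19.

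**The case against.** The strongest reply is that nothing depends on this number. The same part of Section 8.0 analyses both relations by suitable methods, and kappa is nowhere called the measure of association. The analysis is exploratory, in a study that describes itself as exploratory, and no sample size or decision rule uses it. This stands, and it sets the severity.

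A reader might infer more than the documents support in four ways:

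- **That kappa cannot register these associations at all.** In a 2x2 table kappa is exactly 0 under independence and, for a fixed coding, has the sign of the association. It is the magnitude that cannot be interpreted.
- **That kappa would always be near zero for antibodies.** That needs antibodies to be uncommon relative to raised calprotectin. The second table shows ceilings of 0.40 and 0.62 at higher counts.
- **That Fisher's test would succeed where kappa fails.** With 3 antibody-positive subjects, all raised, two-sided Fisher p is 0.059, 0.105, 0.26 and 0.54 for 15, 18, 22 and 26 raised of 37. Sparse data are part of the difficulty in that scenario.
- **That the sentence was copied from the ST2 item.** The wording is similar, but this remains an inference.

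It can also be said that recoding affects any directional measure, since the odds ratio of 0.14 becomes 7.28. That is fair as to sign, and labelled categories settle it. But the odds ratio only inverts, whereas kappa can also change in size (step 5).

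The general mention of kappa in Section 8.0 does not justify it here. That paragraph gives kappa no purpose and names chi-square or Fisher for two categorical variables. The plan itself uses those tests, without kappa, for antibody presence against active or inactive disease.

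**Conclusion.** The point holds, at minor severity. The sentence prescribes an agreement statistic for a pair that does not rate one attribute, whichever pair is meant. Its size would depend on the antibody rate, the chosen cut-offs and the coding: at a fixed odds ratio of 6 it runs from 0.42 to 0.07 as antibodies become rarer. All such figures rest on assumed margins with 37 subjects.

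It would be tempting to conclude that the exposure and immunogenicity findings would be wrong. The documents do not support that, because the correlation and t-test or Mann-Whitney results would be reported alongside. The harm is limited to a misleading supplementary exploratory statistic. Kappa for ST2 against calprotectin is not open to this objection.

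**What to change.** Delete the single kappa sentence that follows the antibody and calprotectin item in Section 8.0, and leave the planned correlation and group comparisons as they are.

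If a categorised analysis is wanted, replace the sentence with one that does the following:

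- names the two variables;
- states the calprotectin cut-off, and the golimumab cut-off if level is used, before the data are examined;
- presents the 2x2 table with labelled categories;
- reports Fisher's exact test, which Section 8.0 already provides for, and an odds ratio with 95% CI. An exact interval is needed because an empty cell, as in the one-way scenarios above, makes the estimate infinite.

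Retain kappa for ST2 against calprotectin only, and say so in the general paragraph of Section 8.0. The cost is a sentence or two of wording, with no new data and no effect on sample size.

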Investigational Product: Golimumab (SIMPONI) sc as per product monograph
Reference Product: Not applicable
STATISTICAL METHODS: All quantitative variables will be summarized through descriptive statistics namely mean, median, standard deviation and range (minimum and maximum) and qualitative variables through absolute (n) and relative frequencies (%) and 95% confidence intervals (if applicable). The statistical analysis will be performed through frequency tables for qualitative variables and tables with descriptive statistics for quantitative variables.  The association between two quantitative variables will be performed through Pearson correlation coefficient or Spearman correlation coefficient, in case the normality assumption was not verified.  The association of two categorical variables will be tested through the Chi-Square test or Fisher Exact test (if applicable). Cohen's kappa coefficient will be performed.  The comparison of two independent samples in respect to quantitative variables will be performed through t-test for independent samples or the Mann-Whitney non-parametric test, according to the assumption validations of the statistical test.  ROC curve analysis will be performed as well as sensitivity, specificity, and positive and negative predictive values.
Data Set(s) to be Analyzed: The primary analysis is to be performed on the Full Analysis Set, defined as all subjects who had received study medication and had at least one valid post baseline assessment for the primary endpoint that correlates ST2 with endoscopic activity. In addition, a Per Protocol Set is defined as subjects receiving treatment, who meet key eligibility and evaluability criteria. Sensitivity analyses will be based on this Per Protocol Set. All safety analyses will be performed on the All Treated Set, comprising all subjects who received at least one dose of study medication.
Sample Size: Based on the recruitment capacity of sites it is expected to include a total of 37 subjects for analysis. With this sample size there is a probability of 80% that the lower limit of a one-sided 95% confidence interval is higher than 0.50, if the observed correlation coefficient is at least

**TITLE OF TRIAL: An open label, single group assignment design study to correlate soluble ST2 with clinical, endoscopic and histological activity in moderate to severe Ulcerative Colitis patients under Golimumab**

(Phase 4; Protocol No. MK 8259-022-03)

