**Study Analysis:**

The primary analysis is to investigate the correlation between serum soluble ST2 and:

- endoscopic activity of disease (measured by endoscopy Mayo subscore) at 6 weeks in UC subjects receiving golimumab;
- histological activity (measured by Geboes index score) at 6 weeks in UC subjects receiving golimumab.

For both analyses the Spearman correlation coefficient will be used.

[figure not shown]
For the key secondary endpoints the following analysis will be performed:

- The correlation between serum soluble ST2 with endoscopic activity of disease (measured by endoscopy Mayo subscore) at 16 weeks in UC subjects receiving golimumab, through the Spearman correlation coefficient;
- The correlation between serum soluble ST2 histological activity (measured by Geboes index score) at 16 weeks in UC subjects receiving golimumab, through the Spearman correlation coefficient.
- Serum soluble ST2 levels at baseline, Week 6 and Week 16 will be correlated with fecal calprotectin levels at baseline, week 6 and week 16 through Pearson correlation coefficient or Spearman correlation coefficient in case the normality assumption is not verified. The two biomarkers will be categorized by the cut-offs and Cohen's kappa coefficient will be obtained.
- Serum soluble ST2 levels at baseline, week 6 and week 16 will be correlated with clinical activity (total Mayo score), through Spearman correlation coefficient.
- Comparative analyses of means (active disease versus inactive disease at week 6) with serum ST2 at baseline and change between baseline and week 6.
- Comparative analyses of subjects who achieved response at week 6 and maintained through week 16 versus subjects who did not maintain response, regarding serum soluble ST2 at baseline, week 6 and change between baseline and week 6. ROC curve analysis of the serum soluble ST2 at week 6 regarding maintenance of response between week 6 and 16 will be performed. This exploratory analysis will detect the cut-off levels of the serum soluble ST2 at week 6 associated with maintenance of response.

**Safety Analysis:** Adverse events and laboratory tests will be analyzed through descriptive statistics.

**Interim Analysis:** No formal interim analyses are planned

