### **7.3.4 Replacement of Subjects**

A subject who discontinues from the study without performing at least one valid post baseline assessment for the primary endpoint correlating ST2 with endoscopic activity may be replaced at the discretion of the sponsor.

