## 8.0 STATISTICAL AND ANALYTICAL PLAN

All quantitative variables will be summarize through descriptive statistics namely mean, median, standard deviation and range (minimum and maximum) and qualitative variables though absolute (n) and relative frequencies (%) and 95% confidence intervals (if applicable). The statistical analysis will be performed through frequency tables for qualitative variables and tables with descriptive statistics for quantitative variables.

The association between two quantitative variables will be performed through Pearson correlation coefficient or Spearman correlation coefficient, in case the normality assumption was not verified.

The association of two categorical variables will be tested through the Chi-Square test or Fisher Exact test (if applicable). Cohen's kappa coefficient will be performed.

The comparison of two independent samples in respect to quantitative variables will be performed through t-test for independent samples or the Mann-Whitney non-parametric test, according to the assumption validations of the statistical test.

ROC curve analysis will be performed as well as sensitivity, specificity, and positive and negative predictive values.

The primary analysis is to investigate the correlation between serum soluble ST2 and:

- endoscopic activity of disease (measured by Endoscopy Mayo subscore) at 6 weeks in UC subjects receiving golimumab, through the Spearman correlation coefficient;
- histological activity (measured by Geboes index score) at 6 weeks in UC subjects receiving golimumab, through the Spearman correlation coefficient.

Additionally, it will be obtained the cut-off of serum soluble ST2 levels at week 6 that optimizes sensitivity and specificity in the identification of disease activity through ROC curve analysis supplemented with analysis of sensitivity, specificity, and positive and negative predictive values. Endoscopic activity will be classified according to endoscopy subscore of Mayo score and histological activity will be classified according to Geboes index score.

For the analysis of the secondary endpoints the following analysis will be performed:

- the correlation between serum soluble ST2 with endoscopic activity of disease (measured by Endoscopy Mayo subscore) at 16 weeks in UC subjects receiving golimumab, through the Spearman correlation coefficient;

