Results for hematology (basophils, eosinophils, hematocrit, hemoglobin, lymphocytes, monocytes, neutrophils, platelets, RBC, WBC); blood chemistry (total bilirubin, ALT, AST, alkaline phosphatase, albumin, total protein, calcium, phosphate, sodium, potassium, chloride, urea and creatinine and CRP; urinalysis (proteins, glucose, nitrates, WBC, ketone bodies, hemoglobin, urobilinogen, bilirubin) will be summarized by total number of observations (n), mean, median, standard deviation, minimum and maximum.

Based on the recruitment capacity of sites it is expected to include a total of 37 subjects for analysis. With this sample size there is a probability of 80% that the lower limit of a one-sided 95% confidence interval is higher than 0.50, if the observed correlation coefficient is at least 0.75.

The primary analysis is to be performed on the Full Analysis Set, defined as all subjects who had received study medication and had at least one valid post baseline assessment for the primary endpoint that correlates ST2 with endoscopic activity.

In addition, a Per Protocol Set is defined as subjects receiving study medication, who meet key eligibility and evaluability criteria (without major protocol deviations). Sensitivity analyses will be based on this Per Protocol Set.

All safety analyses will be performed on the All Treated Set, comprising all subjects who received at least one dose of study medication.

No interim analysis is planned.

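### The sample-size sentence conditions its 80% on the observed correlation instead of the true one; for the planned Spearman coefficient the matching figure is a few points lower and depends on an interval the plan does not name

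*Combined protocol and SAP*

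**What the plan says.** The sample-size paragraph of Section 8 starts from feasibility: "Based on the recruitment capacity of sites it is expected to include a total of 37 subjects for analysis". It then attaches an 80% chance to the following event: "the lower limit of a one-sided 95% confidence interval is higher than 0.50, if the observed correlation coefficient is at least 0.75". The Sample Size entry of the synopsis repeats the condition ("is higher than 0.50, if the observed correlation coefficient is at least", followed by 0.75).

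The coefficient for the two week 6 primaries is fixed. The synopsis says "For both analyses the Spearman correlation coefficient will be used". Section 8 says the same for each primary, for example "endoscopic activity of disease (measured by Endoscopy Mayo subscore) at 6 weeks in UC subjects receiving golimumab, through the Spearman correlation coefficient".

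No interval method or variance is named for a Spearman coefficient. Apart from the sample-size sentence, Section 8 mentions confidence intervals only in its opening sentence on descriptive statistics: "qualitative variables though absolute (n) and relative frequencies (%) and 95% confidence intervals (if applicable".

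**The concern.** A confidence limit for a correlation is a function of the observed coefficient and n. Once both are given, nothing random is left, so a probability of 80% cannot be attached to the limit. The statement makes sense only if 0.75 is the true correlation and the observed value varies around it.

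The wording can mislead in practice. It suggests that a result of 0.75 is needed, and that even then there is a one-in-five chance of a lower limit at or below 0.50. Neither is so.

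The second issue is the coefficient. The 80% matches the usual Fisher z variance for a Pearson correlation. The sampling variance of Spearman's coefficient is somewhat larger, and different approximations to it give different probabilities. This is the plan's only probability statement for its sample size, so it should belong to the estimator that will be used.

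**Working it through.** **Inputs from the documents.** n = 37, one-sided 95% limit (z = 1.645), bound 0.50 and correlation 0.75 (Section 8, sample-size paragraph). Spearman for both primaries (synopsis and Section 8). Endoscopic subscore with four levels, 0 to 3 (Section 7.7.2.2). On the Fisher scale, atanh(0.75) = 0.9730 and atanh(0.50) = 0.5493, a difference of 0.4236.

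**Formulas.** The standard error is sqrt(c/(n-3)) = sqrt(c/34), with c = 1 for Fisher z, 1.06 for the common Spearman adjustment and 1 + r²/2 for Bonett-Wright.

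- Lower limit at observed r: tanh(atanh(r) - 1.645 × SE).
- Probability at true 0.75: Phi(0.4236/SE - 1.645).

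**Step 1: reproduce the plan's 80%.** With c = 1, SE = 1/sqrt(34) = 0.1715. Then 0.4236/0.1715 - 1.645 = 0.825, and Phi(0.825) = 79.5%. The n for exactly 80% is ((1.645 + 0.842)/0.4236)² + 3 = 37.4. A two-sided 95% limit would give 69.5%, which does not match. So the figure is recovered by taking 0.75 as the true value. That the plan used this variance is an inference from the match.

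**Step 2: read the sentence literally.** With c = 1 and observed r = 0.75, the lower limit is tanh(0.9730 - 1.645 × 0.1715) = tanh(0.6909) = 0.599. The limit rises with r, so every observed value of 0.75 or more clears 0.50. The smallest observed r that clears it is tanh(0.5493 + 0.2821) = 0.681. For the 1.06 variance SE = sqrt(1.06/34) = 0.1766; for Bonett-Wright at r = 0.75, SE = sqrt(1.28125/34) = 0.1941.

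| Interval | Lower limit at observed 0.75 | Smallest observed r with limit above 0.50 | Probability at true 0.75, by formula |
|---|---|---|---|
| Fisher z | 0.599 | 0.681 | 79.5% |
| 1.06/(n-3) | 0.593 | 0.686 | 77.5% |
| Bonett-Wright | 0.574 | 0.698 | 70.5% |

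**Step 3: simulate the Spearman coefficient.** 60,000 trials of 37 subjects per scenario, bivariate normal, population Spearman correlation set to 0.75. In the four-level version one variable was cut into scores 0/1/2/3 under five assumed splits. Three of the splits put 42% at 0 or 1, the week 6 mucosal healing rate cited in Section 5.1.

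| Interval | Continuous | Four-level, five splits |
|---|---|---|
| Fisher z applied to Spearman | 76.0% | 78.2–78.7% |
| 1.06/(n-3) | 74.5% | 76.8–77.2% |
| Bonett-Wright | 69.9% | 72.4–72.9% |

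Simulated one-sided coverage at true 0.50 and 0.75 was 94.3–95.0% with the 1.06 variance and 95.8–96.8% with Bonett-Wright. The lowest probabilities therefore come with an interval that is wider than it needs to be.

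**The case against.** The best defence is that one word is wrong and the numbers are not. The values 37, 80%, 0.50 and 0.75 are mutually consistent once 0.75 is taken as the true correlation. Section 5.1 cites an earlier correlation of 0.76 with the endoscopic score, so a statistician would recognise 0.75 as a planning value. That defence stands as far as it goes: there is no slip in the calculation. It does not rescue the sentence, which appears twice and says something else. The same section cites 0.67 for histology, so the parallel reaches only the endoscopic primary.

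A reader might infer that 80% can be reached only with the plain Fisher z variance. That is too strong. Adding the usual bias term 0.75/(2 × 36) = 0.0104 to the difference gives 79.2% with the 1.06 variance. A true correlation of 0.76 with that variance and no bias term gives 81.2%. The shortfall for this interval is within what a change of 0.01 in the assumed correlation would remove.

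It can also be said that leaving the interval unnamed is a missing detail in an exploratory study, not an error, and that the sample-size sentence already implies a lower limit. I accept that description. The detail still matters here, because the probability cannot be stated for Spearman until the interval is chosen.

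**Conclusion.** The sentence is wrong as written and should be corrected in both places. Conditional on an observed correlation of 0.75 or more, the probability is 100%. Conditional on a true 0.75 it is 79.5% with the Fisher z variance. For the planned Spearman coefficient it is modestly lower: 77.5% by formula and about 74 to 77% by simulation with variance 1.06/(n-3), or about 70 to 73% with Bonett-Wright. These are alternative choices, and their gaps from 80% should not be pooled into one shortfall.

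The Spearman figures assume that 0.75 is the population Spearman value and that the data are bivariate normal, or bivariate normal with one variable cut into four levels. They apply to each primary separately. The Geboes score was not simulated; I take the continuous and four-level results as a reasonable guide to it.

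Two stronger readings are not supported:

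- A reader might conclude that the study is too small. The plan says that recruitment capacity sets n, and no test or decision rule uses 0.50.
- A reader might infer that the sentence covers endoscopy alone, because the Full Analysis Set ("had at least one valid post baseline assessment for the primary endpoint that correlates ST2 with endoscopic activity") and the replacement rule in Section 7.3.4 ("at least one valid post baseline assessment for the primary endpoint correlating ST2 with endoscopic activity") name that primary. Those passages settle who is analysed or replaced, not which coefficient the sample-size sentence describes.

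Severity is minor: the effect is limited to how the plan states its precision.

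**What to change.** Keep n = 37. In Section 8 and in the Sample Size entry of the synopsis, make the condition a true Spearman correlation of 0.75, name one Spearman interval, and print the probability that goes with it. For example:

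*With 37 subjects and a true Spearman correlation of 0.75, the one-sided 95% lower limit (Fisher z, variance 1.06/(n-3)) exceeds 0.50 with probability about 75–77% for each primary taken separately; an observed correlation of about 0.69 or higher gives such a limit.*

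If the sponsor prefers Bonett-Wright, the matching figures are about 70–73% and an observed 0.70, with slightly conservative coverage. Either choice is defensible if it is made before the data are analysed.

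Add to the primary analysis text that each of the two Spearman coefficients will be reported with this lower limit.

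The cost is a rewording in two places, one added sentence and one extra number per primary. No patients, visits or procedures are added. The downside is that the stated probability becomes a few points less favourable with the 1.06 variance, and more so with Bonett-Wright.
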